## STUDY DESIGN

EM/PROTECT, a behavioral intervention for depressed elder mistreatment (EM) victims, was designed to work in synergy with EM mistreatment resolution services that provide safety planning, support services, and links to legal services. PROTECT is built on a model which postulates that chronic stress promotes dysfunction of the cognitive control (CCN) and reward networks, impairing the victims' ability to flexibly respond to the environment and limits their rewarding activities. PROTECT therapists work with EM victims to develop action plans to reduce stress, and to increase rewarding experiences. EM/PROTECT has been designed in an iterative process with community EM providers of the New York City (NYC) Dept. for Aging (DFTA) to use agencies' routine depression screening and referral for service. We propose to collect data on feasibility and acceptability of EM/PROTECT. We will compare the effectiveness and target engagement of EM/PROTECT with EM enriched with training of EM staff in linking EM victims to mental health services (EM/MH) in order to position us for a fully powered R01. To ensure rigor and reproducibility, EM/PROTECT or EM/MH will be offered to randomly assigned depressed EM victims, and standardized assessments will be conducted by trained raters blind to participant assignment and our hypotheses. The training of staff and therapists will follow high standards of intervention fidelity. EM staff will screen using routine standardized measures and refer depressed victims to study staff who will describe the study and obtain consent and conduct research assessments. We will use brief validated instruments to assess the outcomes, explore the added value of mobile technology measures, and study the effect of sex in each aim. The EM agencies of NYC are overseen and funded by DFTA. We will Page 22 of 34 5/9/19 1:02 PM begin by working with the Elderly Crime Victims Resource Center (ECVRC), as we have successfully partnered with them in the past for our initial exploratory work ([name] et al., 2015a and b). We will then work with DFTA to identify a second site. At both sites we will provide refresher training in depression screening and strategies for linking victims to mental health using the Open Door approach we jointly developed with DFTA. Randomization at the participant level will be conducted by the Methods Core (random numbers in blocks of varying size). Both agencies will conduct depression screening. EM workers will not be blind to treatment arm. We are aware that their knowledge of treatment assignment may influence the EM services they provide. For this reason, we will record and compare their services between the two treatment arms to inform the design of the R01 proposal that will follow this R34 study.

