
The primary objective of the EM/PROTECT project will be to evaluate the effectiveness of EM/PROTECT compared to EM/MH. We also propose to examine the reach, feasibility, and acceptability of EM/PROTECT for depressed EM victims. 1) Effectiveness: In both conditions, the reduction of clinically significant depressive symptoms (as measured on the Montgomery Asberg Depression Rating Scale [MADRS]) and improved quality of life. 2) Reach: In both conditions, number of clients screened vs. all eligible for screening, and clients who meet study criteria. 3) Feasibility: Number of victims who initiate EM/PROTECT, number of EM/MH victims who make contact with mental health services, number who attend research procedures. EM/PROTECT: session completion rate; smartphone use. 4) Acceptability: Victims satisfaction (CSQ) in both treatments; EM/PROTECT session completion at 6, 9, 12, and 16 weeks.

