We plan to recruit 4.5 subjects per month over 14 months to achieve a final sample of 80 subjects. We will recruit 2 licensed clinical social workers to administer the PROTECT therapy sessions with clients. The larger number of EM/PROTECT participants will allow a better view of effectiveness and reach/feasibility/acceptability. Effectiveness objective: In separate linear mixed models, we will analyze primary (MADRS, WHOQOL assessed at baseline, 6, 9 and 12 weeks) and secondary measures of effectiveness (PAM, ratings of mood and anhedonia assessed daily) with a subject-specific random intercept and slope and fixed effects for time, treatment, EM agency, LCSW, treatment x time interaction. We will use model building and fitting strategies. In the final model, we will also estimate end of treatment improvements in outcome (from baseline) within each treatment group. As Page 24 of 34 5/9/19 1:02 PM this is an inadequately powered R34 study, we will control for false discovery rate using the Benjamini-Hochberg approach, and not the Family-Wise Error Rate, to adjust for multiple comparisons of secondary outcomes. The focus of our analysis would be to obtain preliminary signals of effectiveness by estimating effect sizes (95% CI) and assessing clinical relevance. Using approaches of Initiative 2.1 (Methods Core), we will conduct exploratory joint analysis of primary and secondary longitudinal outcomes. We will also test between group differences in smartphone measures using the time series approach of Initiative 2.1 (Methods Core). Reach/feasibility/acceptability objective: We will calculate estimates and 95% CI of the following measures for all subjects and for each sex separately. Reach: Proportions screened and met study criteria in both conditions. Feasibility: Among EM/PROTECT clients, proportions of: treatment drop-outs, assessment completions, smartphone use. Proportion of EM/MH victims who contacted mental health services. Acceptability by clients: We will analyze victim satisfaction (CSQ) recorded at baseline, 6, 9, 12 and 16 weeks as in Aim 4. Benchmark tests of feasibility (75% session attendance rate and 70% smartphone ratings) and acceptability will be performed using one-sample z-test of proportions.

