PROTOCOL TITLE: EM/PROTECT: Improving Depression in Elder Mistreatment Victims

PRINCIPAL INVESTIGATOR: [name] [name], PhD, Weill Cornell Medicine

IRB Protocol #: 1703018101

ClinicalTrials.gov Identifier: NCT03241225

Current Version: November 24, 2021

Descriptive statistics for continuous (median and interquartile range; IQR) and categorical (frequency and percentage) were reported on demographics and clinical characteristics of two treatment groups at baseline. A Mann-Whitney test and Fisher's exact test were conducted to test the difference between PROTECT and Usual care for continuous and categorical variables, respectively.

Remission rate was defined as the percentage of participants with MADRS scores  $\leq 10$  at Week 9. Response was defined as a reduction of  $\geq 50\%$  in MADRS scores from baseline to Week 9. We conducted two mixed-effects linear regression models to compare the trajectories of change in MADRS scores and WHOQOL scores between PROTECT and Usual care, respectively. Each model included fixed effects of treatment (PROTECT vs. Usual care), time, and their interaction, as well as a participant-specific random intercept. Both models were adjusted for age and gender. Site and its interaction with treatment were initially included in the model but were dropped as their effects were statistically non-significant. A two-sided p-value less than 0.05 was considered statistically significant. Intent-to-treat analyses are presented with all available data in the mixed-effects models. Remission and response rates were calculated based on 30 patients with complete data. All analyses were conducted in R 3.6.1 (R Foundation for Statistical Computing; <http://www.r-project.org/>).

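### Week 9 remission and response are calculated only in 30 patients with complete data, so they leave out partly followed patients whom the mixed models keep

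*SAP*

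**What the plan says.** The SAP introduces remission with "Remission rate was defined as the percentage of participants with MADRS scores" of 10 or less at Week 9. Response is a fall of at least half in MADRS from baseline to Week 9. On the analysis set there are two adjacent statements. For the continuous outcomes: "Intent-to-treat analyses are presented with all available data in the mixed-effects models". For the two binary outcomes: "Remission and response rates were calculated based on 30 patients with complete data". The SAP does not say whether complete data means baseline and Week 9 or every visit. It gives no missing-data method for these rates.

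The protocol (STUDY DESIGN) plans recruitment "to achieve a final sample of 80 subjects", with more participants in EM/PROTECT than in the comparison arm. Its reach/feasibility/acceptability analysis lists "Among EM/PROTECT clients, proportions of: treatment drop-outs, assessment completions, smartphone use". For EM/MH the only feasibility proportion there is contact with mental health services. The feasibility objective in the same section also lists "number who attend research procedures", with no limit to one arm and no stated split by arm.

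**The concern.** The definition of remission is worded for participants in general, but the calculation uses completers. A patient seen at baseline and Week 6 but not at Week 9 contributes to the MADRS mixed model and is absent from the remission rate. The continuous and binary MADRS results may therefore describe different groups of patients.

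A likelihood-based mixed model uses the partial follow-up and is valid if loss depends only on observed data. A completer proportion discards that follow-up. It is generally biased for the rate among all randomised when loss depends on earlier MADRS, even where the mixed model is not.

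The protocol describes its purpose as follows: "The focus of our analysis would be to obtain preliminary signals of effectiveness by estimating effect sizes (95% CI) and assessing clinical relevance", and the comparison is made "in order to position us for a fully powered R01". Remission and response are the results in the SAP that classify each patient's MADRS outcome, and someone planning the larger trial may well reuse them.

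**Working it through.** **Inputs from the documents.** 30 patients with complete data (SAP); 80 subjects planned, at 4.5 per month for 14 months (Protocol, STUDY DESIGN). The 30 is an observed count and cannot be reproduced, because the documents do not give the number randomised, the arm sizes or the number lost. Everything below rests on assumed inputs.

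**1. What share could the 30 be?** If N were randomised, the complete share is 30/N. The rate among all N could then lie anywhere in a band of width (N − 30)/N, depending on the unseen outcomes.

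| Assumed N | Basis | 30/N | Band width, points |
|---|---|---|---|
| 80 | planned sample | 37.5% | 62.5 |
| 63 | 4.5 × 14 | 47.6% | 52.4 |
| 40 | assumed | 75.0% | 25.0 |
| 36 | assumed | 83.3% | 16.7 |
| 30 | no loss | 100% | 0 |

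**2. Difference between arms.** Assume 40 randomised as 24 EM/PROTECT and 16 comparison (the protocol plans the larger arm for EM/PROTECT but gives no ratio), 30 complete, and 50% remission among completers in both arms. The completer difference is then 0 in every row. Count missing as non-remission:

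| Complete, EM/PROTECT and comparison | EM/PROTECT | Comparison | Difference, points |
|---|---|---|---|
| 18 of 24 and 12 of 16 | 9/24 = 37.5% | 6/16 = 37.5% | 0 |
| 20 of 24 and 10 of 16 | 10/24 = 41.7% | 5/16 = 31.3% | +10.4 |
| 14 of 24 and 16 of 16 | 7/24 = 29.2% | 8/16 = 50.0% | −20.8 |

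Equal proportional loss lowers both rates and leaves the difference at zero. Unequal loss moves the difference in either direction. These rows take every lost patient as a non-remitter, which is an extreme assumption.

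**3. Loss linked to the Week 6 score.** Assume Week 6 MADRS has mean 16 and SD 8, Week 9 MADRS has mean 14 and SD 8, and the two are bivariate normal. Remission is a Week 9 score of 10 or less. Patients outside the worst third at Week 6 miss Week 9 with probability 10%. Completer remission minus true remission, in points, by simulation with 2,000,000 draws:

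| Correlation | 30% of worst third missing | 50% | 70% |
|---|---|---|---|
| 0.5 | 1.5 | 3.2 | 5.3 |
| 0.7 | 2.1 | 4.4 | 7.3 |
| 0.8 | 2.3 | 5.0 | 8.1 |

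The true rate is Φ((10 − 14)/8) = Φ(−0.5), about 30.8%. In the central case completers show 35.2%. Overall loss in the three columns is 16.7%, 23.3% and 30.0%.

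**4. The same mechanism in both arms.** With no treatment effect, the bias in the difference is 0.0. With an assumed 4-point MADRS benefit the true difference is Φ(0) − Φ(−0.5), about 19 points, and the bias is −2.0 to +3.0 points over the same grid. For scale, with 15 per arm and 40% remission the standard error of a difference is √(2 × 0.4 × 0.6/15), about 18 points. A shared mechanism thus mainly inflates the level of each rate, and a large bias in the difference needs loss that differs by arm.

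**The case against.** The effectiveness analysis is the pair of mixed models, which keep all available data. Remission and response do not appear in the protocol text available. The SAP states the restriction to 30 openly, does not call these rates intent-to-treat and names no between-arm test of them. The protocol's sentence on effect sizes sits with the mixed models, so its link to these rates is an inference. Complete data also has a natural reading, a baseline and a Week 9 score, and under it the same 30 might come back. All of this stands, and it limits the importance of the point.

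A reader might infer that attrition in the comparison arm goes unrecorded, so that unequal loss was hidden. The documents do not support that. The feasibility objective counts research attendance without limiting it to one arm. The list for EM/PROTECT is a set of intervention-feasibility measures, and treatment drop-out is not the same as a missing Week 9 MADRS. Counts by arm are results, which a short methods text need not carry. What remains is narrower: assessment completion is planned as a proportion for EM/PROTECT only, and the general attendance count has no stated split by arm.

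The objection does not answer the main point. Using completers for these two rates is a stated analysis choice, and a less bias-prone estimate can be made from data already held.

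**Conclusion.** The concern holds in a limited form. Week 9 remission and response discard partly followed patients whom the mixed models retain, so the rates can be biased if loss depends on earlier MADRS, and their difference can be biased if loss differs by arm. The actual size and direction cannot be determined without the number randomised and the arm split of the 30.

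Under the assumed Week 6 mechanism, each rate is inflated by 1.5 to 8.1 points. The difference moves by −2.0 to +3.0 points when the arms share the mechanism and there is a 4-point benefit. It moves by +10.4 or −20.8 points in the assumed examples of unequal loss with every missing patient a non-remitter. It would be a further step to conclude that the reported rates are wrong or favour one arm. The documents do not show that loss was unequal, or how large it was. If loss was small and balanced, the counts alone will show it. The MADRS and WHOQOL mixed models are unaffected. This is a cheap improvement.

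**What to change.** Label all of the following post hoc, since the SAP describes finished analyses.

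- Define the completer set as everyone with both a baseline and a Week 9 MADRS. Give numerators and denominators by arm beside the number randomised in each arm, and call the results completer rates.
- Add remission and response for all randomised, using multiple imputation of Week 9 MADRS from arm, baseline MADRS, available follow-up MADRS, age and gender. This rests on a missing-at-random assumption like that of the mixed model.
- As one simple sensitivity check, count missing as non-remission and non-response.

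No further tests are needed. The cost is a short table of counts and a rerun of two binary summaries from data already held, with no change to the mixed models. The downside is that imputed estimates will be imprecise in a sample this small, and the report should say so.
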